8.4 Vital Signs

Blood pressure and pulse are assessed at Screening, predose on Day 1 and on Days 14 and 28. Respiratory rate, temperature and pulse oximetry are measured at Screening and on Days 14 and 28.

Summary statistics will be calculated for all vital sign parameters by timepoint and treatment. Change from baseline (Predose Day 1) for blood pressure and pulse will be summarized for post baseline by timepoint and treatment. Baseline is defined as the result closest and prior to first dose on Day 1 which may include unscheduled or recheck results. Postdose unscheduled event and recheck results will not be included in summaries.

8.5 12-Lead Electrocardiogram

12-lead electrocardiogram (ECG) will be assessed at Screening and Days 14 and 28 for HR, RR, PR, QRS, QT and QTcF. All ECG parameters will be listed by subjects with QTcF>450 msec flagged. Summary statistics will be calculated for each parameter and presented by timepoint and treatment. Postdose unscheduled event and recheck results will not be included in summaries.

8.6 Concomitant Medications

All concomitant medications recorded during the study will be coded with the WHO Dictionary March 2018 B3 and listed.

8.7 Physical Examination

Full physical examinations will be performed at Screening and on Days 14 and 27. Symptom driven physical examination may be performed at other times, at the PI or designee's discretion. All data found in the CRF will be listed.

8.8 The Columbia-Suicide Severity Rating Scale (C-SSRS)

C-SSRS will be administered at Screening, Day 14 and Day 27. Results recorded on the CRF will be listed.

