6 SYNOPSIS

Compound:	S 48168 (ARM210)
Clinical Indication:	Ryanodine receptor 1-related congenital myopathy (RYR1 -RM)
Study Phase and Type:	Phase 1 – Safety and Tolerability, pharmacokinetic (PK), and pharmacodynamic/target engagement (PD/TE)
Primary objective:	
To determine safety and tolerability of S 48168 (ARM210) treatment in RYR1-RM affected individuals.
 
Hypothesis: S 48168 (ARM210) treatment will have no safety concerns that limit further development and will be generally well tolerated in RYR1-RM patients.
 
Primary endpoint: Composite safety and tolerability profile (Frequencies of the following: TEAEs \geq grade 2 in severity (CTCAE version 5), all SAEs, and all AESIs).
 
Methods: Safety and tolerability of S 48168 (ARM210) will be determined by monitoring Adverse Events (AEs) over approximately 28 (not to exceed 30) days of treatment via patient interviews, patient diary reviews, physical examinations, echocardiograms, electrocardiograms (ECGs), vital signs, and laboratory safety tests. A reference dataset of AEs/SAEs obtained from a natural history study of RYR1-RM will also be available to assist in interpretation of safety events. The Columbia-Suicide Severity Rating Scale (C-SSRS) will be administered pre- and post-intervention. The frequency and severity of AEs will be compared between treatment and historical controls including a previously conducted natural history study at the NIH.

Exploratory objectives:	
1. To determine PK of a 28 day (not to exceed 30-day) administration of S 48168 (ARM210) in RYR1-RM affected individuals.

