- d: Samples for serum chemistry will be obtained following a fast of at least 10 hours, however, in case of dropouts or rechecks, subjects may not have fasted for 8 hours before the serum chemistry sample is taken. FSH and HbA1c are only required at screening.
- e: AE's will be monitored throughout the study. Study Investigators will attempt to contact all subjects who received at least one dose of study drug (including subjects who terminate the study early) using their standard procedures on Days 7 and 21 (\pm 2 days) whilst on study drug and on Days 35 ± 2 and 42 ± 2 (Follow-up) to determine if any AE has occurred since the last study visit. A compliance assessment will be conducted as a part of the Day 7 and Day 21 contact. Subjects will enter daily log of symptoms as well as study drug intake in a diary for the days when direct communication is not done.
- f: To be performed within 24 hours prior to dosing.
- g: Baseline 24hr PK will only be conducted on study drug naïve individuals.
- h: Prior to dosing.
- i: Participants will return to NIH CC on Day 27 for scheduled events. Participants will be observed and examined one day post cessation of dosing, for any withdrawal effects. Administration of the final dose and 24 hour PK will occur following approximately 28 days dosing (not to exceed 30 days).
- j: Approximately 14 days (\pm 2 days) following cessation of S 48168 (ARM210), participants will have follow-up safety laboratory tests.

Abbreviations: Admin = Administration, AE = Adverse event(s), C-I = Check-in, Chem = Chemistry, CYP = Cytochrome P450, FU = Follow-up, HIV = Human immunodeficiency virus, NIH CC = National Institutes of Health Clinical Center, PI = Principal Investigator, PK = Pharmacokinetics.

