A study investigator will contact participants by telephone weekly when not on site to remind them of upcoming, scheduled local phlebotomy appointments and perform remote TEAE assessments, if applicable.

The final onsite study visit (Day 42 ± 2 Days) will consist of muscle/motor function assessments, PROMIS-fatigue questionnaire, AE assessment, vital signs, physical examination, safety labs, and a blood draw.

Daily subject diaries will be used to capture both time of dose administered as well as any symptoms they may feel in between remote TEAE assessments.

Confinement, Return Visits, and Follow-Up

Participants will be admitted to the NIH CC on the evening of Day -1 for drug administration. Drug naïve participants will undergo baseline 24hr PK sample collection the next morning.

Participants will attend a phone call on Day 14 (± 2 days). This will include review of any concomitant medication, TEAE assessment, and C-SSRS and PROMIS-fatigue questionnaires. Safety labs will be obtained remotely or at NIH CC if the participant is local to the study site.

Participants will return to the NIH CC on Day 28 (± 1 day) for repeat safety labs, PE, ECG, vital signs, and a 24hr PK sample collection.

Participants will return to the NIH CC for Day 42 ± 2 days for vital signs, AE assessment, exploratory efficacy assessments, safety labs, and a blood draw.

At all times, a subject may be required to remain at the NIH CC for longer at the discretion of the Principal Investigator (PI) or designee (e.g. when deemed necessary for safety reasons).

Participants will be contacted by telephone/secured email for a follow up regarding TEAEs approximately weekly when not on site and will also have a blood draw for safety clinical laboratory tests at day 14. This will include participants who terminate the study early. Participants local to the study site will have the option of completing AE assessments and safety clinical laboratory tests at the NIH.

Participants will also be able to enter any symptoms they experience in a participant diary (Appendix # 6).

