12.10 Safety Assessments

Safety and tolerability of S 48168 (ARM210) will be determined by monitoring Adverse Events (AEs) over approximately 28 days (not to exceed 30 days) of treatment via physical examinations, electrocardiograms (ECGs), vital signs, and laboratory safety tests. A reference dataset of AEs/SAEs obtained from a natural history study of *RYR1*-RM will also be available to assist in interpretation of safety events. Per FDA requirements for a drug with a novel mechanism that has not been evaluated in patients, the Columbia-Suicide Severity Rating Scale (C-SSRS) (Appendix # 15) will be administered pre- and post-intervention. The frequency and severity of AEs will be compared between treatment and historical controls including a previously conducted natural history study at the NIH.

The aggregate review of AEs, discontinuations and other safety findings from diaries and AE monitoring, will determine participant tolerability. A participant will be considered to have tolerated a dose if the participant experiences no clinically significant drug-related AE or laboratory abnormality. Conversely, a participant will not be considered to have tolerated the dose if he/she experiences a clinically significant drug-related AE or laboratory abnormality during the study drug administration or post-administration follow-up period. Clinically meaningful changes in vital signs (heart rate, blood pressure, and breathing rate) and cardiac function tests (ECGs and echocardiography) will be assessed by the medical monitor in conjunction with investigators. Further interpretation of such tests by a specialist (e.g. cardiologist) may be requested if deemed necessary by the medical monitor and PI.

S 48168 (ARM210) has been safe and well tolerated to date. However, in normal healthy volunteers, there is not likely to be an effect on muscle function. In patients with *RYR1*-RM,

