12.10.5 The Columbia-Suicide Severity Rating Scale (C-SSRS)

The C-SSRS is a suicidal ideation and behavior assessment instrument. The FDA recommends assessment of suicidal ideation and behavior for all clinical trials where the drug has central nervous system activity per Guidance for Industry Suicidal Ideation and Behavior: Prospective Assessment of Occurrence in Clinical Trials. Although S 48168 (ARM210) at this dose will have minimal brain penetration, the requirement extends to novel mechanisms that have not previously been evaluated in patients.

The C-SSRS is a detailed interview, but the full interview is needed only if the initial screening questions about suicidal ideation and behavior are positive. Although the screening questions should be completed at baseline and at every visit for every patient, they are not by themselves burdensome, typically taking only 1 to 2 minutes for patients who have no positive findings. Even for a patient with multiple positive findings, the full interview typically takes less than 10 minutes. Investigators administering the C-SSRS will be required to have completed training provided by The Columbia Lighthouse Project: <http://cssrs.columbia.edu/training/training-research-setting/>.

Management of participants positive for suicidal ideation and behavior:

- Result of C-SSRS is positive for suicidal ideation and behavior
- Principal Investigator is informed of the positive C-SSRS
- NIH Psychiatry Service is consulted
- Participant is managed in accordance with standard clinical care and suicide risk assessment. This may include social work consultation, referral to local psychiatric care, or psychiatric admission when clinically indicated.

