2.2 Endpoints

Primary:

Composite safety and tolerability profile

(Frequencies of the following: TEAEs \geq grade 2 in severity (CTCAE version 5), all SAEs, and all AESIs).

Methods: Safety and tolerability of S 48168 (ARM210) will be determined by monitoring Adverse Events (AEs) over 28 days of treatment via patient interviews, patient diary reviews, physical examinations, echocardiograms, electrocardiograms (ECGs), vital signs, and laboratory safety tests. A reference dataset of AEs/SAEs obtained from a natural history study of RYR1-RM will also be available to assist in interpretation of safety events. The Columbia-Suicide Severity Rating Scale (C-SSRS) will also be administered pre- and post-intervention. The frequency and severity of clinically significant AEs will be compared between treatment and historical controls including a previously conducted natural history study at the NIH.

Exploratory:

1. To determine PK of a 28-day administration of S 48168 (ARM210) in RYR1-RM affected individuals.

Endpoints:

Day 1: AUC_{0 t}, AUC_{0 inf}, C_{max}, T_{max}, and t_{1/2}

Day 28: AUC_{tau}, C_{max}, T_{max}, C_{min}, RAAUC, and RAC_{max}

Secondary PK parameters will include: AUC₀₋₂₄, AUC%extrap, T_{min}, K_{el}, T_{lag}, and Day 13 C_{trough} (associated with Day 14 pre-dose). Additional parameters may be calculated as appropriate.

Methods: Bloods for PK assessments will be drawn at baseline (Day 0, 24h PK), at the study mid-point (day 14 \pm 2 days, trough PK), and at the final study visit (Day 28, 24h PK). Whole blood will be processed, and the plasma fraction stored for batch PK analyses.

2. To explore if S 48168 (ARM210) treatment increases RyR1-calstabin1 binding in skeletal muscle of RYR1-RM affected individuals.

Endpoint: Change from baseline in relative RyR1-calstabin1 binding (AU) and (pending sufficient tissue yield) change from baseline in relative Fluo-4 signal (AU).

Methods: Skeletal muscle tissue will be obtained from participants pre- and post-intervention by needle biopsy. This tissue will be assessed for RyR1-calstabin1

binding by co-immunoprecipitation followed by protein detection. The percentage of Calstabin1 binding to RyR1 pre-dose will be compared to the percentage obtained post-dose in each patient. Pending sufficient tissue yield, muscle membrane preparations may be assessed for changes in calcium permeability (Fluo-4 signal) using a thapsigargin assay.

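### Protocol 12.10.5 calls for the C-SSRS at every visit, but the flow chart and SAP 8.8 stop at Day 27, so none is scheduled after the final dose or at the Day 42 visit

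*SAP*

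**What the plan says.** Three places promise the scale without giving a day. The Protocol Synopsis says "The Columbia-Suicide Severity Rating Scale (C-SSRS) will be administered pre- and post-intervention". Protocol 12.10 repeats this and ties it to an FDA requirement for a novel mechanism not yet studied in patients. SAP 2.2 says "The Columbia-Suicide Severity Rating Scale (C-SSRS) will also be administered pre- and post-intervention".

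Protocol 12.10.5, the section on the instrument itself, gives a frequency: "the screening questions should be completed at baseline and at every visit for every patient".

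SAP 8.8 gives days: "C-SSRS will be administered at Screening, Day 14 and Day 27". The results are to be listed. The flow chart in Protocol section 7 marks suicidality twice in its first half (at screening and once later) and once in its second half, with nothing under follow-up.

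On the end of dosing, flow chart footnote i has participants return on Day 27 and take the final dose after about 28 days of treatment, with 30 as the limit. It adds "Participants will be observed and examined one day post cessation of dosing, for any withdrawal effects". Under Amendment 5 the Day 42 visit is on site. Protocol 11.1 says it "will consist of muscle/motor function assessments, PROMIS-fatigue questionnaire, AE assessment, vital signs, physical examination, safety labs, and a blood draw".

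For early withdrawal, Protocol 11.6.3 schedules a local blood sample and a remote TEAE assessment at about 7 days, and a further remote TEAE assessment at about 14 days. It does not mention the C-SSRS.

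**The concern.** Two parts of the plan give different schedules for one safety instrument. Site staff work from the flow chart and programmers from the SAP. If both follow those documents, the frequency in 12.10.5 is not carried out, and the *since last visit* C-SSRS listings in the SAP will hold nothing from the off-drug period.

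That period is one the protocol chose to watch. Section 12.10 adds post-dose monitoring because participants may improve on drug and return to baseline afterwards. The Précis has the efficacy measures repeated after withdrawal. As scheduled, the trial would collect fatigue scores off drug but no suicidality data at the same visit.

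**Working it through.** No sample size, power or error rate is involved. The check sets the passages side by side and counts days.

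**1. Timing of the C-SSRS by source**

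| Source | Timing given | Covers Day 42? |
|---|---|---|
| Protocol Synopsis and 12.10; SAP 2.2 | Before and after the intervention, no day | Depends on the meaning of the term |
| Protocol 12.10.5 | Baseline and every visit | Yes, read literally |
| Protocol 11.1 | Named for the Day 14 phone call; not named in the Day 28 or Day 42 lists | Not named |
| Protocol flow chart | Two marks in the first half, one in the second, none under follow-up | No |
| SAP 8.8 | Screening, Day 14, Day 27 | No |

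The single mark in the second half of the flow chart lines up with weight and the full physical examination. SAP 8.7 puts that examination on Day 27, which agrees with SAP 8.8.

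**2. Day count**

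- Last scheduled C-SSRS: Day 27. Final dose: about Day 28, at the latest Day 30.
- Last C-SSRS to final dose: 28 − 27 = 1 day, or 30 − 27 = 3 days if dosing runs to the limit and the C-SSRS stays on Day 27.
- Last C-SSRS to final visit: 42 − 27 = 15 days. With the ± 2 day window, 40 − 27 = 13 to 44 − 27 = 17 days.
- Nominal time off drug by the final visit: 42 − 28 = 14 days.
- Scheduled C-SSRS assessments after the final dose: 0 of 3.
- On-site visits with a scheduled C-SSRS: 2 of 3 (before dosing and at end of dosing).

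**3. Other rows of the flow chart**

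Five rows carry a mark at end of dosing and another at the final follow-up: graded functional testing, MFM-32, grip/pinch, quantitative muscle assessment and quality of life. The suicidality row has only the first of these.

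**4. Meaning of *post-intervention***

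- End of dosing: the Précis says these measures will be repeated after withdrawal, so they come before it. SAP 2.2 applies the term to the functional tests and MFM-32, and SAP 8.2 schedules those on Day 27 and labels them post-treatment.
- Time off drug: Protocol 11.2 counts 1, 7 and 14 days post-intervention, and 12.10.7.8 uses the term for the Day 42 contact.

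**5. Early terminators**

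A participant withdrawn before the Day 14 contact has no scheduled C-SSRS after baseline.

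**6. Physical examination**

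Of the two Day 42 lists in Protocol 11.1, one includes a physical examination and the other does not. The flow chart shows none at follow-up. SAP 8.7 lists Screening and Days 14 and 27, although Day 14 is now a phone call.

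**The case against.** A reader might infer that the promised post-intervention assessment never takes place, and that the trial cannot report such a result. The documents do not support that. On the usage in the Précis and SAP 8.2, the Day 27 C-SSRS is the post-intervention one and the promise is met. The opposite usage in 11.2 and 12.10.7.8 makes the term ambiguous, which is a narrower point. Nor does the protocol plainly exclude the scale at Day 42, since 12.10.5 read literally includes it.

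The evidence of omission also has limits. The visit lists in 11.1 are not complete: the Day 28 list leaves out the C-SSRS and the motor tests, although the SAP schedules both on Day 27. The flow chart's columns do not read cleanly in the public text, so the day of its second-half mark is inferred. The SAP predates Amendment 5 more generally. Its section 3 still has a mid-treatment inpatient visit and a remote contact 14 days after the last dose, so its silence on Day 42 is not evidence of a decision.

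The off-drug days are not unmonitored. TEAE assessments take place at about Days 35 and 42, and the protocol describes both open-ended and focused questions. It expects no more than a return to baseline function and describes minimal brain penetration. Participants withdrawn for safety may receive closer monitoring.

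These points limit the claim but do not remove it. The conflict between 12.10.5 and SAP 8.8 does not depend on the visit lists, and the absence of any follow-up mark in the suicidality row does not depend on exact columns. TEAE questioning is not the C-SSRS.

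**Conclusion.** The C-SSRS schedule contradicts itself. Section 12.10.5 gives every visit, while the flow chart and SAP 8.8 give three assessments, all before the final dose. As scheduled, the roughly 14 off-drug days and the Day 42 visit have no C-SSRS, and the last one is about 15 days before study end.

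This rests on nominal days, on reading the flow chart's last suicidality mark as Day 27 (supported by SAP 8.7 and 8.8), and on Day 42 counting as a visit. The Synopsis and 11.1 make it one, although 12.10 and 12.10.7.3 still describe a remote contact.

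The finding is an inconsistency with a practical consequence for safety data. It does not show a missing post-intervention result, and it says nothing about whether mood effects are likely after withdrawal. It should be corrected while participants remain to be treated.

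**What to change.** - **Schedule.** Reconcile the flow chart, Protocol 11.1 and SAP 8.8 with Protocol 12.10.5. Applying 12.10.5 as written puts the brief *since last visit* screen at Day 42. If the sponsor and investigator intend otherwise, 12.10.5 should say so.
- **Term.** State which assessment is the post-intervention one, and use the term the same way in the Synopsis, 11.2, 12.10, 12.10.7.8 and SAP 2.2 and 8.2.
- **Early terminators.** State in 11.6.3 and SAP 8.8 whether they have a C-SSRS at a follow-up contact. The Day 14 phone call already includes the scale, so remote use is feasible.
- **Physical examination.** Make the two Day 42 lists in 11.1, the flow chart and SAP 8.7 agree. Remove the Day 14 examination from SAP 8.7 for participants whose Day 14 is a phone call; any examinations already done at earlier on-site Day 14 visits can still be listed.
- **Remote wording.** Update 12.10, 12.10.7.3 and SAP section 3, which still describe a remote contact about two weeks after the last dose.

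The cost is wording in both documents. By the protocol's own estimate the screen takes one to two minutes for a participant with no positive findings, and typically under ten minutes for the full interview. No visit is added. The SAP already has titles for the *since last visit* listings, and their CRF shells are still to be completed. The change cannot supply off-drug C-SSRS data for participants already past Day 42; the report should say so.

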8.9 Pulmonary Function Test

Each participant will perform pulmonary function testing (PFTs) to assess vital capacity (VC) at screening. Results recorded on the CRF will be listed.

8.10 Medical and Surgical History

All medical and surgical history recorded during the study will be coded with the MedDRA 21.0 and listed.

9. SUMMARY OF CHANGES FROM PROTOCOL-PLANNED ANALYSIS

The analyses described in this SAP are aligned with those analyses described in the protocol.

10. SUMMARY TABLES AND FIGURES

Summary tables and figures are numbered following the International Conference on Harmonization (ICH) structure but may be renumbered as appropriate during the compilation of the tables and figures for the CSR. Note that all summary tables and figures will be generated using SAS® Version 9.3 or higher, as appropriate.

10.1 In-text Summary Tables and Figures

The following is a list of table and figure titles that will be included in the text of the CSR. Tables and figures will be numbered appropriately during compilation of the CSR.

Section 10:

Table 10-1 Subject Disposition Summary

Section 11:

Table 11-1 Demographic Summary

Table 11-2 Summary of Plasma S 48168 (ARM210) Pharmacokinetics Following Single Dose of 120 mg, 200 mg, and 240 mg S 48168 (ARM210) (Treatments A, B, C, and D) (Day 1)

Table 11-3 Summary of Plasma S 48168 (ARM210) Pharmacokinetics Following Single Dose of 120 mg, 200 mg and 240 mg S 48168 (ARM210) (Treatments A, B, C, and D) (Days 14 and 28)

Figure 11-1 Arithmetic Mean Plasma S 48168 (ARM210) Concentration-Time Profiles of Following Single Dose Administration of 120 mg, 200 mg,

and 240 mg S 48168 (ARM210) on Day 1 (Treatments A, B, C, and D) (Linear Scale)

Figure 11-2 Arithmetic Mean Plasma S 48168 (ARM210) Concentration-Time Profiles of Following Single Dose of 120 mg and 200 mg S 48168 (ARM210) in Patients (Day 28) and 120 mg and 240 mg S 48168 (ARM210) in Healthy Subjects (Day 14) (Linear Scale)

Note to Programmer: For Figures 11-2 superimpose both the Days 14 (Healthy) and 28 (Patient). All figures are to be generated in color.

Section 12:

Table 12-1 Adverse Event Frequency by Treatment - Number of Subjects Reporting the Event (% of Subjects Dosed)

